9.7.2 Final Analysis

The final analysis will occur once all participants complete their end of study visit or their last scheduled assessment per the Schedule of Assessments ([Table 3](#)), or the sponsor terminates the study for any reason.

10 STUDY DOCUMENTATION

10.1 Access to Source Documents

In compliance with local regulations and ICH GCP guidelines, it is required that the investigator and institution permit authorised representatives of the sponsor, the regulatory agency(s), and the HREC/IRB direct access to review participants' original medical records for verification of study-related procedures and data. Direct access includes examining, analysing, verifying, and reproducing any records and reports that are important to the evaluation of the study. The investigator is obligated to inform the participant and obtain their consent to permit named representatives to have access to his/her study-related records without violating the confidentiality of the participant.

10.2 Protocol Amendments

No changes (amendments) to the protocol may be implemented without prior approval from the sponsor and the appropriate HREC/IRB, except where necessary to eliminate an immediate hazard to participants. If a protocol amendment requires changes to the Participant Information and Consent Form/Informed Consent Form (PICF/ICF), the revised PICF/ICF must be approved by the HREC/IRB.

10.3 Protocol Deviations

If any issue relating to the safety of the participant arises which requires a deviation from the protocol, the study unit through the investigator may immediately make such a deviation (protocol breach). If there is a need for such a deviation, the study unit must notify the sponsor and the responsible HREC/IRB of the facts and circumstance causing the deviation. Protocol deviations that occur specifically due to the COVID-19 outbreak will be clearly coded as such.

Serious protocol breaches must be reported as per local regulatory requirements. The nature and reasons for the protocol deviations will be recorded by the sponsor.

The sponsor may not reimburse the investigator for cases in which the study procedures and evaluations are conducted such that they result in major protocol violations.

11 QUALITY ASSURANCE AND QUALITY CONTROL

11.1 Audit and Inspection

Study centres and study documentation may be subject to quality assurance audit during the course of the study by the sponsor or its nominated representative. In addition, inspections may be conducted by regulatory authorities at their discretion.

11.2 Monitoring

Data for each participant will be recorded on a case report form (CRF). Data collection must be completed for each participant who signs a PICF/ICF and is enrolled in the study.

In accordance with the ICH GCP guidelines, the study monitor will carry out source document verification at regular intervals to ensure that the data collected in the CRF are accurate and reliable.

The investigator must permit the monitor, the HREC, the sponsor's internal auditors, and representatives from regulatory authorities' direct access to all study-related documents and pertinent hospital or medical records for confirmation of data contained within the CRFs.

12 ETHICS

12.1 Human Research Ethics Committee/Institutional Review Board Approval

The protocol will be submitted for approval to the appropriate HREC/IRB. Prior to initiation of the study, the investigator must provide the sponsor with a copy of the written HREC/IRB approval of the protocol and study PICF/ICF. This approval letter will identify the study PICF/ICF by date and the study protocol by protocol number, title and date. The investigators will receive all the documentation needed for submitting the present protocol to the HREC/IRB. The composition of the HREC/IRB will also be provided to the sponsor. If approval is suspended or terminated by the HREC/IRB, the investigator will notify the sponsor immediately.

It is the responsibility of the sponsor to report study progress to the HREC/IRB as required or at intervals not greater than 1 year.

The investigator at the study site or his/her nominee, will be responsible for reporting any SAEs to the HREC/IRB as soon as possible, and in accordance with the guidelines of the HREC/IRB.

12.2 Regulatory and Ethical Consideration

Relevant study documentation will be submitted to the regulatory authorities of the participating countries, according to local/national requirements, for review and approval before the beginning of the study. On completion of the study, the regulatory authorities will be notified that the study has ended.

The investigator will ensure that this study is conducted in full compliance with the protocol, the Declaration of Helsinki, the ICH GCP guidelines, Federal Drug Administration (FDA)/Therapeutic Goods Administration (TGA) regulations, and all other applicable local laws and regulations. Compliance with these standards provides assurance that the rights, safety, and well-being of patients are protected.

In agreeing to the provisions of the protocol, these responsibilities are accepted by the investigator.

12.3 Informed Consent Process

The process of obtaining informed consent must be in accordance with applicable regulatory requirement(s) and must adhere to ICH GCP guidelines.

The investigator is responsible for ensuring that no participant undergoes any study related examination or activity before that participant has given written informed consent to participate in the study.

The investigator or designated personnel will inform the participant of the objectives, methods, anticipated benefits and potential risks and inconveniences of the study. The participant should be given every opportunity to ask for clarification of any points s/he does not understand and, if necessary, ask for more information. At the end of the interview, the participant will be given ample time to consider the study. Participants will be required to sign and date the PICF/ICF. After signatures are obtained, the PICF/ICF will be kept and archived by the investigator in the investigator's study file. A signed and dated copy of the PICF/ICF will be provided to the participant or their authorised representative.

It should be emphasised that the participant may refuse to enter the study or to withdraw from the study at any time, without consequences for their further care or penalty or loss of benefits to which the participant is otherwise entitled. Participants who refuse to give or who withdraw written informed consent should not be included or continue in the study.

If new information becomes available that may be relevant to the participant's willingness to continue participation in the study, a new PICF/ICF will be approved by the HREC/IRB (and regulatory authorities, if required). Participants will be informed about this new information and reconsent will be obtained.

13 REPORTING AND PUBLICATION, INCLUDING ARCHIVING

Essential documents are those documents that individually and collectively permit evaluation of the study and quality of the data produced. After completion of the study (end of study defined as the date of the last visit of the last participant), all documents and data relating to the study will be kept in an orderly manner by the investigator in a secure study file. This file will be available for inspection by the sponsor or its representatives. Essential documents should be retained for 2 years after the final marketing approval in an ICH region or for at least 2 years since the discontinuation of clinical development of the investigational product. It is the responsibility of the sponsor to inform the study centre when these documents no longer need to be retained. The investigator must contact the sponsor before destroying any study related documentation. In addition, all medical records and other source documentation will be kept for the maximum time permitted by the hospital, institution, or medical practice.

The sponsor must review and approve any results of the study or abstracts for professional meetings prepared by the investigator(s). Published data must not compromise the objectives of the study. Data from individual study centres in multi centre studies must not be published separately.

14 FINANCING AND INSURANCE

Financing of this study will be outlined in a separate agreement.

Participants may be compensated for the time that they spend participating in the study using a formula determined by the study site.

The Investigator is required to have adequate current insurance to cover claims for negligence and/or malpractice. The Sponsor will provide insurance coverage for the clinical study as required by national regulations.

DMC	Data Monitoring Committee
ECG	Electrocardiogram
eCRF	Electronic case report form
EDC	Electronic data capture
ICH	International Council for Harmonisation of Technical Requirements for Pharmaceuticals for Human Use
ICU	Intensive care unit
ITT	Intent-to-treat
LCIQ	Long COVID informant questionnaire
LCQ	Long COVID questionnaire
MedDRA	Medical Dictionary for Regulatory Affairs
MI	Myocardial infarction
mITT	Modified Intent-to-treat
MMRM	Mixed model repeated measures
PHQ	Patient health questionnaire
PP	Per protocol
PT	Preferred term
Q1	1 st quartile
Q3	3 rd quartile
SAE	Serious adverse events
SAF	Safety population
SAP	Statistical analysis plan
SC	Subcutaneous
SD	Standard deviation
SE	Standard error
SofC	Standard of Care
SOC	System organ class
TEAE	Treatment Emergent Adverse Event
WHO	World Health Organization
WHODD	WHO Drug Dictionary

1 INTRODUCTION

The statistical analysis plan (SAP) details the planned statistical analysis methods required to address the study objectives as described in protocol INB03-COVID-19_01: A Multicenter, Double-Blind, Randomized, Placebo-Controlled Trial of INB03 in the Treatment of Participants with Pulmonary Complications from Coronavirus Disease (COVID-19).

This SAP should be read in conjunction with the study protocol and case report form (CRF). The version of this SAP is based on the protocol INB03-COVID-19_01, version 12.0 – 17May2021, and CRF version 16.2 – 02Mar2021. Changes to these documents may result in subsequent changes to the SAP. The final, sponsor-approved version of the SAP will be finalized prior to performing the interim analysis of efficacy. SAP updates may be performed subsequent to that analysis. If this occurs, the SAP will be amended and changes to the approved SAP will be listed in Section 1.1 and the amended SAP will be finalized and approved prior to final database lock and unblinding.

1.1 Changes to the Planned Analysis

The protocol mentions a supplemental analysis will be performed on the ITT population. This analysis will not be performed on this population as the objective of the study is to assess the effect study treatment has on disease progression and patients in the ITT population include those that were randomized but not dosed.

The following sensitivity analyses to assess different strategies for handling intercurrent events have been removed from the analysis as the tipping point analysis will be sufficient in determining robustness of imputation methodologies applied.

- Participants who withdraw consent and have missing disease progression data: The “Composite” strategy will be used. Participants will be considered as having disease progression.
- Participants who withdraw consent and have missing disease progression data: Participants randomized to Placebo will use the “While on Treatment” strategy for this event as described for the primary estimand and participants randomized to INB03 will use the “Composite” strategy.

On 15Jun2021, the sponsor terminated enrollment into the study. A preliminary analysis of the primary efficacy data will be performed prior to full database lock. The SAP was written based on the protocol dated 17May2021 therefore some sections of the SAP may no longer be applicable. Changes from the SAP and protocol defined analyses will be described and justified in the final clinical study report.

2 STUDY OBJECTIVES AND ENDPOINTS

Objectives	Endpoints
Efficacy	
Primary	

 To evaluate if INB03 given as a SC injection can decrease disease progression defined as death or requirement for mechanical ventilation in participants with pulmonary complications from COVID-19 infection 	
 Proportion of participants with disease progression from randomization to 28 days post-randomization, where disease progression is defined by the development of need for mechanical ventilation or death. Mechanical ventilation includes CPAP, BIPAP or mechanical ventilation requiring intubation
Secondary	

 To assess the effect INB03 has on all-cause mortality in participants with pulmonary complications from COVID-19 infection 	
 Proportion of participants with all-cause mortality

 To determine if INB03 can decrease non-respiratory catastrophic complications of COVID-19 infection including admission to ICU, new onset neurologic, cardiovascular or thromboembolic disease, or renal failure 	
 Proportion of participants who transfer to ICU level care by Day 28 (ICU level care is defined as a hospital setting where patient to nurse ratio is < 4) Proportion of participants with a new onset of neurologic disease (requiring medical intervention), including stroke by Day 28 Proportion of participants with evidence of new CHF or new MI requiring medical intervention by Day 28 Proportion of participants with a new onset embolus or thrombus by Day 28 Proportion of participants who develop a need for renal replacement therapy (defined as need for any type of dialysis including intermittent or continuous peritoneal or hemodialysis) by Day 28

 To evaluate if treatment with INB03 reduces increase in the WHO Ordinal Scale for Clinical Improvement score 	
 Proportion of participants with an increase in the WHO Ordinal Scale of Clinical Improvement score at any time during the study

 To evaluate if length of hospital-stay in participants with pulmonary complications from COVID-19 infection decreases when treated with INB03 	
 Length of hospital stay defined as the number of days in hospital from time of randomization to time of discharge or death, whichever occurs first

 To assess the effect INB03 has on inflammatory markers in participants with pulmonary complications from COVID-19 infection 	
 Change from baseline in inflammation markers over time
Safety	

 To evaluate the safety and tolerability of INB03 when given to participants with pulmonary complications from COVID-19 infection 	
 Incidence of adverse events and serious adverse events not due to underlying disease Incidence of abnormal findings in clinical safety laboratory parameters, vital signs, and ECGs

Exploratory	
Efficacy	

To qualitatively and quantitatively evaluate the presence and nature of residual (post-Study Day 40) complaints of fatigue, malaise, affective symptoms, inflammatory cognitive dysfunction syndrome and associated functional limitations	
Percentage of participants who report Long COVID symptomsTotal score on the Patient Health Questionnaire-9 (PHQ-9)Total and subscale scores on Long COVID Questionnaire (LCQ)Total and subscale scores on Long COVID Informant Questionnaire (LCIQ)

3 STUDY DESIGN

3.1 General Description

The trial is a Phase 2, double-blind, placebo-controlled, randomized clinical trial of INB03 in participants with pulmonary complications from COVID-19 infection. Each participant will complete up to 6 study visits.

Screening: Participants with a diagnosis of COVID-19 will be screened for study eligibility. Prior to any trial related procedures, participants will provide their consent to participate in the clinical trial. Screening assessments that are performed as part of routine clinical care within 1 day of Screening do not need to be repeated.

Study Day 1: Eligible participants will be randomized to receive either INB03 at 1mg/kg by subcutaneous injection (SC) + standard of care (SofC) or Placebo SC injection + SofC within 1 day of Screening. Participants will receive their first dose of study drug after randomization. Blood samples to check TNF levels and perform an anti-drug antibody test will be collected before dosing. Clinical assessments while participants are inpatients will be as per routine management of hospitalized COVID-19 patients including daily collection of vital signs, physical exam, concomitant medications (including SofC) and laboratory evaluations. 12-lead ECGs and chest imaging assessments will be performed if deemed clinically necessary. Additionally, use of non-mechanical ventilation will be collected daily until the participant is discharged from hospital.

The WHO Ordinal Scale will also be completed daily until the participant is discharged from hospital.

Study Day 8: Participants will be given a second dose of INB03 or Placebo on Day 8 (7 days after randomization) if they remain in hospital. Clinical assessments while participants are inpatients will continue as per routine management of hospitalized COVID-19 patients.

Since the timing of hospital discharge in this patient population cannot be predicted, discharge assessments will be obtained on the day the participant is to be discharged. If the participant remains in the hospital, the participant will continue with daily assessments as per the Schedule of Assessments (SOA) (Table 3 in the protocol). At discharge, no additional follow-up is expected until the participant is seen for the Study Day 28 visit.

Study Day 28: A follow-up visit will be conducted on Day 28. If participant is still in hospital at Study Day 28, no additional follow-up is expected until the participant is seen on the Day 40 final safety visit.

Study Day 40: A final visit will be conducted on Day 40. End of study safety assessments will be conducted as per the SOA (Table 3 in the protocol).

Study Day 40-50: Participant will complete Long COVID questionnaires using an electronic Patient-Reported Outcomes (ePRO) portal. Assessments will include the Patient Health Questionnaire-9 (PHQ-9) and a Long COVID questionnaire (LCQ). The LCQ is a composite questionnaire that assesses Function and Performance, somatic and cognitive complaints reported to be associated with Long COVID syndrome. Additionally, the questionnaire captures life changes associated with COVID societal restrictions that existed or were anticipated prior to and *independent* of the participant's COVID-19 disease.

The Long COVID Informant questionnaire (LCIQ) will be completed by an informant, defined as someone who has known the participant for at least two years and interacts (face to face or via phone) for at least 4 hours per week beginning prior to contracting COVID-19, in person at the Study Day 40 visit or by phone. A separate informed consent form will be collected from the informant prior to completion of this questionnaire.

Study Day 50-70: In a subset of participants who report Long COVID symptoms, a telephone interview will be conducted by a third-party neuropsychologist to qualitatively and quantitatively evaluate the presence and nature of residual (post-Study Day 40) or emergent complaints of fatigue, malaise, affective symptoms, inflammatory cognitive dysfunction syndrome and associated functional limitations. This interview will consist of a semi-structured interview and open-ended questions to catalogue residual complaints which will be subjected to concept matching exercises to estimate the need for amending the LCQ to capture COVID-19 specific residuum. The interview time is estimated to be 45 minutes. Data captured during the semi-structured interviews will be de-identified and stored securely in electronic format.

Study Day 70: Participants will be contacted via telephone on Day 70 to assess AEs and changes in concomitant medications.

3.2 Randomization and Blinding

Participants who meet inclusion and exclusion criteria and sign informed consent are to be randomized within 1 day of completing screening assessments. Participants will be randomized 1:1 on Study Day 1 in a blinded fashion to either treatment with INB03 at 1 mg/kg + SofC or Placebo + SofC.

Due to the complexity of COVID-19 and the need for immediate randomization, each site pharmacist has been provided with a separate randomization schedule unique to the specific site. The pharmacist at each site is unblinded and is responsible for providing the randomization number to site personnel who further record this information in the electronic case report form (eCRF).

3.3 Sample Size

A total sample size of 366 participants randomized 1:1 to treatment with either INB03 + SofC or Placebo + SofC (N=183 in each arm) will provide adequate power to compare the proportion of participants with disease progression in each group by Day 28. It is assumed that 21% of enrolled participants randomized to Placebo + SofC will progress whereas the expected disease progression rate will be reduced by two-thirds to 7% in participants randomized to INB03 + SofC. To observe the expected treatment effect, N=346 (N=173 per arm) are required.

Additionally, an interim analysis for futility will be performed once approximately 20% of participants required to observe the expected treatment effect complete the Study Day 28 visit (approximately N=70). Participants evaluated in the interim analysis include those who are randomized and receive study drug and have the Day 28 assessment or who had an intercurrent event prior to Day 28. A customized futility boundary was chosen to ensure a clinically meaningful difference between treatment arms is observed at the interim and which will provide a high conditional power at the time of the final analysis.

The proposed study with the above assumptions will have at least 90% power assuming a one-sided Z-Test with overall alpha for the study of 0.005.

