9.7 Analysis and Reporting

9.7.1 Interim Analyses

An interim analysis will be performed when approximately 70 participants in the mITT population have completed the Study Day 28 assessment or who have an intercurrent event within 28 days on study (withdrawal or lost to follow-up). Imputation of missing data will be performed as described in [Section 9.5.1](#).

Efficacy data, including the primary endpoint and cumulative safety data will be reviewed at the time of the interim analysis by the DMC.

A non-binding one-way futility analysis will be performed. The futility boundaries were derived using custom Z-statistic. The Z-statistic chosen as the boundary is considered clinically relevant and has a high probability of success at the final analysis with conditional power of at least 81.5%. At the time of the interim analysis, the Z-statistic boundary was chosen based on a 7.5% treatment difference corresponding to a placebo event rate of 20% and INB03 event rate of 12.5%. The futility boundary will be set at $Z < -0.8505$ (one-sided test). Should the result of the primary endpoint analysis Z-statistic be greater than -0.8505 (one-sided p-value ≥ 0.1975), the futility boundary will be considered crossed, and futility assumed. At the time of interim analysis, the boundary may be recalculated based on true number of participants with evaluable data included in the interim analysis population.

In order to maintain the study blind, an independent unblinded statistical team not involved in the conduct of the study will perform the analyses and present the results to the DMC during a closed meeting where only the DMC members and the unblinded statistician attend.

A preliminary analysis of the primary efficacy data will be performed prior to the final database lock. The primary efficacy endpoint will be analyzed and a limited number of individuals who are not involved in the study conduct or review of day-to-day activities of the study will be informed on the unblinded efficacy results in order to plan further development and inform on other corporate objectives. The DMC will also review unblinded safety and the primary efficacy data and recommend to the sponsor their unbiased opinion concerning safety and efficacy of INB03 in an acute COVID population.

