6.2.4 Interim Analysis

An interim analysis will be performed once approximately 70 patients (20% of information) in the mITT population have completed the Study Day 28 assessment or who have an intercurrent event within 28 days on study leading to missing primary efficacy data. All patients up to the data cutoff date for the interim analysis will be included in the analysis. Imputation of missing data will be performed as described in Section 6.2.1.3.

Efficacy data, including the primary endpoint, and cumulative safety data will be reviewed at the time of the interim analysis by the DMC.

A non-binding one-way futility analysis will be performed. The futility boundaries were derived using custom Z-scores. The Z-score chosen as the boundary is considered clinically relevant and has a high probability of success at the final analysis with conditional power of at least 81.5%. At the time of the interim analysis, there must be at least a 7.5% treatment difference observed. Assuming the placebo event rate of 20% and INB03 event rate of 12.5%, the futility boundary will be set at $Z < -0.8505$ (one-sided test). Should the result of the primary endpoint analysis Z-statistic be greater than -0.8805 (one-sided p-value ≥ 0.1975), the futility boundary will be considered crossed, and futility assumed. At the time of interim analysis, the boundary may be recalculated based on true number of participants with evaluable data included in the interim analysis population.

In order to maintain the study blind, an independent unblinded statistical team not involved in the conduct of the study will perform the analyses and present the results to the DMC during a closed

meeting where only the DMC members and the unblinded statistician attend. Details included in the DMC charter.

The futility analysis is non-binding and the DMC will make a recommendation based on review of primary efficacy and safety data. The DMC will recommend the trial continue as planned or be terminated due to futility or safety concerns. There will be no early termination due to positive efficacy signals. The decision to terminate the trial will be at the sole discretion of the sponsor.

On 15Jun2021, the sponsor terminated enrollment into the study. Participants who were enrolled and randomized on or before 15 June were followed to study completion and will be included in the primary efficacy analysis. A total of 79 subjects were randomized, 77 receiving randomized study drug.

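### The stated power of at least 90% is the value without a futility stop; it is about 77% if the non-binding futility rule is followed and, separately, about 20% at the 77 participants dosed

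*SAP*

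**What the plan says.** SAP 3.3 gives the design assumptions: "It is assumed that 21% of enrolled participants randomized to Placebo + SofC will progress", with the rate "reduced by two-thirds to 7% in participants randomized to INB03 + SofC". The test is a "one-sided Z-Test with overall alpha for the study of 0.005". On size it says: "To observe the expected treatment effect, N=346 (N=173 per arm) are required". It then describes the futility interim and closes with "The proposed study with the above assumptions will have at least 90% power assuming a one-sided Z-Test". Protocol 9.1 follows the same order and repeats the power claim.

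Protocol 9.7.1 and SAP 6.2.4 define the interim rule. The trial continues without a futility signal only if Z is below -0.8505; otherwise, in the protocol's words, "the futility boundary will be considered crossed, and futility assumed". The SAP prints a second value, -0.8805, in the sentence that defines crossing. Both documents call the rule non-binding, leave the recommendation to the DMC and the decision to the sponsor, and allow the boundary to be recalculated. The only probability of success given for the interim is a conditional power of at least 81.5%.

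SAP 1.1 and 6.2.4 report that the sponsor ended enrolment on 15 June 2021. SAP 6.2.4 adds: "A total of 79 subjects were randomized, 77 receiving randomized study drug". SAP 1.1 warns that parts of the plan may no longer apply and defers changes to the clinical study report.

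SAP 6.2.1 keeps the primary test at one-sided 0.005, and SAP 5.1 sets a default two-sided 1% level. SAP 6.2.1.2 plans only a 95% interval for the primary comparison.

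**The concern.** The power sentence is attached to the proposed study, and that study has a futility look that can stop it. A futility look can only lower power. This one is demanding, because it asks for a clear trend in favour of INB03 after about a fifth of the participants. Neither document says how much power is lost if the rule is obeyed.

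The second issue is the size reached. The SAP was updated after enrolment ended, but its only power figure still belongs to 346 participants. SAP 6.2.4 plans to show the unblinded primary result to selected sponsor staff for development planning. A non-significant result read against a 90% figure looks like evidence that the drug does not work. Read against a figure near 20%, it says little either way.

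The third issue is smaller. A 95% interval can exclude no effect while the one-sided 0.005 test fails, so interval and test can appear to disagree.

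**Working it through.** **Inputs.** Rates 0.21 and 0.07, 173 per arm (183 randomized), and one-sided alpha 0.005, so z = 2.576 (SAP 3.3). Interim at about 70, taken as 35 per arm, with boundary -0.8505 (SAP 6.2.4, protocol 9.7.1). 77 dosed (SAP 6.2.4). Z is written below as placebo minus INB03, so continuing means Z > 0.8505.

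**1. The plan's 90%, with no interim.**
- Standard error under the null: √(2 × 0.14 × 0.86 / 173) = 0.0373. Under the alternative: √((0.21 × 0.79 + 0.07 × 0.93) / 173) = 0.0365.
- Pooled formula: Φ((0.14 − 2.576 × 0.0373) / 0.0365) = Φ(1.20) = 88.5%.
- Unpooled formula: Φ(0.14 / 0.0365 − 2.576) = Φ(1.26) = 89.5%.
- Exact binomial enumeration: 90.2% for the pooled Z, 89.9% for a CMH-type statistic.
- Allowance for untreated participants: 346 / 0.95 ≈ 365, consistent with 366.

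The 90% reproduces as a fixed-design value.

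**2. The boundary and the 81.5%.**
- 20% versus 12.5% at 35 per arm: 0.075 / √(2 × 0.1625 × 0.8375 / 35) = 0.8505, one-sided p = 0.1975. The p-value belongs to -0.8505; Φ(-0.8805) = 0.189.
- Conditional power at the boundary, with information fraction t = 70/346 = 0.2023 and drift θ = 0.14 / 0.0373 = 3.75, is Φ((0.8505√t + θ(1 − t) − 2.576) / √(1 − t)) = 81.5%. This assumes that the remaining data follow 21% versus 7%. If they follow the trend seen at the boundary, it is about 22%.

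The 81.5% is conditional on sitting at the boundary. It is not the power of the design.

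**3. Power if the futility rule is followed.** This is the probability that interim Z > 0.8505 at 35 per arm and final Z ≥ 2.576, under 21% versus 7%.

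| Method | Final n per arm | Boundary | P(stop) | Power |
|---|---|---|---|---|
| Exact, pooled Z | 173 | -0.8505 | 17.3% | 77.1% |
| Exact, CMH-type | 173 | -0.8505 | 19.1% | 75.4% |
| Normal approximation (drift 3.75-3.83) | 173 | -0.8505 | 19-20% | 73-75% |
| Exact, pooled Z | 183 | -0.8505 | 17.3% | 78.0% |
| Exact, pooled Z | 173 | -0.8805 | 19.4% | 75.4% |

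A simulation of 1,000,000 trials gives 77.2% for the first row. The loss on the exact pooled Z is 90.2 − 77.1 ≈ 13 points.

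**4. Power with 77 dosed.** The documents do not give the split; 38 placebo and 39 INB03 is assumed.
- Normal approximation: 20.8% pooled, 22.0% unpooled.
- Exact: 18.1% pooled Z, 17.4% CMH-type.
- Splits of 37/40 and 40/37 move the exact pooled and CMH-type values to between 16.0% and 21.3%. An unpooled Z evaluated exactly at 38/39 gives 23.9%, but the CMH statistic uses a null-based variance.
- Precision: the standard error of the risk difference at the assumed rates is √(0.21 × 0.79 / 38 + 0.07 × 0.93 / 39) = 0.0777. The half-width is 1.96 × 0.0777 = 15 points for a 95% interval and 2.576 × 0.0777 = 20 points for a 99% interval, against an assumed difference of 14 points.
- Illustration: 8/38 versus 3/39, close to the assumed rates, gives Z = 1.68 and one-sided p = 0.047, which does not meet 0.005.

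**5. Interval against test.** For 10/38 versus 3/39, the Wald 95% interval for INB03 minus placebo is -0.35 to -0.02, which excludes zero. The one-sided p is 0.015, which fails 0.005. The 99% interval, -0.40 to 0.03, agrees with the test.

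**The case against.** A reader might infer that the 90% was miscalculated. It was not: step 1 reproduces it, and the protocol synopsis derives 346 from 90% power before it introduces the interim. The fault is an unstated condition.

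A reader might also infer that the design could only ever deliver 77%. The documents do not support that. The rule is non-binding, the sponsor decides, and the boundary may be recalculated, so 77% is the case of full compliance. If the rule is overridden, 90% stands. The condition still needs stating, because both documents say that futility is assumed on crossing.

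It can be said that the 77% no longer matters because enrolment has ended. It does not describe the trial as it finished, and it must not be run together with the figure for 77 participants: one assumes enrolment to 346, the other a stop at 77. It remains the missing condition on a sentence that the SAP still prints.

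Nor does the SAP hide the shortfall. SAP 1.1 and 6.2.4 disclose the termination and the numbers, and warn that some sections may not apply. Keeping a planning sample size as planned is normal practice. But the warning names no section and gives no revised power or precision.

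Finally, the 95% intervals can be defended as descriptive, and the decision rule itself is clear. That is fair; the 99% interval is an aid to reading. No passage says that a non-significant result will be taken as no effect, so that risk is one of interpretation.

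**Conclusion.** The point holds as an omission in the power statement. About 90% is the fixed-design value. With the non-binding rule followed, power is about 77% (73-78% by method and final size; about 75% with the other printed boundary), and the chance of stopping a drug that works as assumed is about 17% (up to 20% by method). Separately, at the 77 dosed, power for the assumed effect is about 17-22%, and no revised figure is given.

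These results assume equal arms at the interim, a 38/39 split of the 77, unstratified tests and the design rates of 21% and 7%. Stratification, merging of strata and imputation would shift them somewhat. The documents do not say that enrolment ended because the futility boundary was crossed, and nothing here should be read as implying it.

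**What to change.** - In SAP 3.3, label 90% as the planning value for the fixed design without futility stopping. Add that power is about 77% if the non-binding rule is followed.
- In the SAP or the clinical study report, give power of about 20% for the 77 dosed, or the expected interval width, using the actual split. State that a non-significant primary test is not evidence of no effect.
- Report a two-sided 99% interval beside the 95% interval for the primary comparison, to match SAP 5.1 and 6.2.1.
- Reconcile -0.8505 and -0.8805 in SAP 6.2.4.

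SAP section 1 allows amendment before final lock and unblinding. The cost is a less favourable stated power, a few sentences and one more interval. No further participants are needed.
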